1.0 Project Summary/Abstract

The **objective** of this research project is to evaluate hip muscle function among lower limb prosthesis users, its contribution to balance and mobility, and the effect of prosthetic socket design on amputated limb hip muscle strength and endurance. Traditional socket designs can provide pelvic support that interferes with hip motion. They may also reduce the effort required from amputated limb hip muscles to stabilize the hip and amputated limb, risking further loss of muscle mass and strength beyond that due to amputation. Long-standing use of sockets with pelvic support may therefore intensify amputated limb muscle loss and weakness, leading to challenges with walking and balance, increasing the effort required to walk, and contributing to degenerative changes in the hips and knees.

2.0 Background/Scientific Rationale

Residual limb hip muscle weakness is a pronounced, consequential, and modifiable deficit among prosthesis users that is not adequately understood. After amputation residual limb hip muscles undergo structural changes, such as atrophy^{1,2,3} and fatty infiltration^{4,3}, causing pronounced muscle weakness^{2,5-7}. These changes are not observed with the same frequency or magnitude in the intact leg⁵, suggesting they are due to amputation¹³ and/or socket design⁹ rather than general deconditioning⁵. Assessments of residual limb strength have, to date, however been limited to non-fatiguing conditions, and measures of maximum voluntary strength^{2,5,6}. Important functional aspects of strength including the rate of force development, which is essential to balance¹⁰⁻¹¹, and muscular endurance, which is crucial to mobility^{12,31} and strenuous tasks like load carriage¹², have been overlooked. Additionally, a number of major residual limb hip muscles and relevant covariates (e.g., etiology) remain untested. As a result, we do not have a full understanding of the force generating capacity of residual limb hip muscles in transfemoral prosthesis users that is required to assess the effect of socket design on residual limb hip muscle function. To address this gap a comprehensive evaluation of residual limb hip muscle strength and endurance is needed.

Preliminary evidence suggests residual limb hip muscle weakness is a consequential deficit among transfemoral prosthesis users. Muscle weakness has been associated with gait abnormalities^{1,13}, secondary degenerative disorders (e.g., joint degeneration)¹⁴, increased metabolic cost of gait^{15,16}, as well as reduced mobility^{17,18} and balance confidence¹⁹. Causal links however between residual limb hip muscle function and balance or mobility remain poorly understood among transfemoral prosthesis users²¹. Preliminary statistical modeling of causal relationships between residual limb hip muscle function and walking and balance performance is needed to address this gap.

Fortunately, residual limb hip muscle weakness appears to be a modifiable, and thus a treatable deficit in transfemoral prosthesis users. Gains in residual limb hip muscle strength have been observed in lower limb prosthesis users after only moderate strength training (8-12 weeks; 2/week)^{15,19,21}. Whether socket design has a similar modifying effect on residual limb hip muscle strength is unknown, but presents an appealing opportunity. The prospect of increasing residual limb hip muscle strength and endurance simply by walking with a different socket design is attractive because it could be accomplished in a patient's own home, community, and workplace, without additional equipment (i.e., environment and activity specific strength training). Our prior results and anecdotal reports support a study to quantify changes in residual limb hip muscle function in lower limb prosthesis users wearing different sockets.

3.0 Objectives/Aims

The objective of this study is to assess residual limb hip muscle function in lower limb prosthesis users, understand its role in balance and mobility, and the effect of socket design on residual limb hip muscle function. Our central hypothesis is that the residual limb is weaker than the intact limb as well as controls, and that socket design alters hip muscle function. To address this objective and central hypothesis, we will assess the following specific aims:

Aim 1: Evaluate hip muscle function and its contribution to balance and mobility among unilateral lower limb prosthesis users. We hypothesize that: i) the strength and endurance of hip muscles on the residual limb will be lower than on the intact limb, and of age- and sex-matched able-bodied persons, and ii) muscular strength and endurance will not differ between the intact limb and age- and sex-matched able-bodied persons. To test these hypotheses hip muscle strength and endurance will be measured using a motor-driven dynamometer. Lower peak torque and rates of torque development will be taken as evidence of reduced strength, while a larger decrease in average work at the end of an isokinetic fatigue protocol will be taken as evidence of reduced endurance. Secondarily, we will also collect balance and mobility outcomes data (e.g., Four Square Step Test, PLUS-M, step counts, and fall history), and use regression methods to explore the contributions of hip muscle strength and endurance to balance and mobility in lower limb prosthesis users.

Aim 2: Test whether socket design alters hip muscle function among lower limb prosthesis users. We hypothesize that walking with different socket designs will: i) require different residual limb hip muscle activity, as evidenced by greater peak muscle activity, as well as altered onset and offset times, and ii) result in short- and long-term gains in residual limb hip muscle strength and endurance, as evidenced by an increase in average peak torque, rate of torque development, and resistance to fatigue. To test these hypotheses electromyographic signals will be recorded from hip muscles on the residual limb of unilateral lower limb prosthesis users walking at a range of speeds. Hip muscle strength and endurance will be measured using a motor-driven dynamometer. Assessments will be made at baseline in established wearers of an ischial containment socket, and then again at eight and 42-weeks after being fit with a sub-ischial socket. Step count activity data will be collected to determine the extent to which gains in residual limb hip muscle strength and endurance are due to changes in hip muscle activation versus an increase in physical activity.

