12.0 Statistical Considerations

Descriptive statistics: Measures of central tendency and variation will be used to describe participant characteristics, and all study variables (e.g., balance and mobility tests, muscle strength). Normality, homogeneity of variance, and multicollinearity will be evaluated using the Shapiro-Wilk test, Levene's test, and, Pearson's r (r<.90) respectively. If assumptions are met data will be analyzed with parametric tests, otherwise non-parametric tests will be used. Statistical analyses will be performed using SPSS 25 (Chicago, IL).

Aim 1: A 2-way mixed-MANCOVA (multiple analysis of covariance), or non-parametric equivalent, will be used to test for statistically significant differences in strength and endurance between legs (prosthetic, intact, and control) as well as across muscle groups while controlling for potential covariates (e.g., residual limb length, etiology). Multiple linear regression will be used to determine how much variation (i.e., difference) in balance and mobility outcomes (e.g., Four Square Step Test; physical activity) among transfemoral prosthesis users can be explained by differences in hip muscle strength and endurance.

Aim 2: As a pilot study, descriptive analyses including measures of central tendency (mean) and dispersion (95% confidence intervals), along with effect sizes (e.g., Cohen's d, common

language effect size), will be used to evaluate changes in residual limb hip muscle activity, strength, between test sessions while controlling for covariates. Correlation analyses will be used to determine if any observed changes in hip muscle strength can be attributed to changes in hip muscle activity (i.e., EMG) or physical activity (i.e., step count).

Power Analysis: Choosing a power of 0.80 and a type I error rate (α) of 0.05, pilot data from lower prosthesis users (n=2) and able-bodied persons (n=2) estimate that a sample of 20 people per group will be sufficient to identify differences (p<0.05) in hip muscle strength and endurance between the residual limb, intact limb, and able-bodied persons using a mixed analysis of variance (ANOVA) (Aim 1). As a pilot study, enrollment in Aim 2 will be limited to 10 unilateral lower limb prosthesis users.

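### Aim 1 hypothesis (ii) claims no intact-control difference, but the only planned limb comparison is an omnibus test for differences that names no such contrast and cannot support it when non-significant

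*Combined protocol and SAP*

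**What the plan says.** Section 3.0, Aim 1, sets out two numbered hypotheses. The second is that "muscular strength and endurance will not differ between the intact limb and age- and sex-matched able-bodied persons". Both are presented as claims to be tested: "To test these hypotheses hip muscle strength and endurance will be measured using a motor-driven dynamometer". The section then says how results will be read, but in one direction only. "Lower peak torque and rates of torque development will be taken as evidence of reduced strength", with a parallel rule for reduced endurance. It gives no rule for what would count as evidence that limbs do not differ.

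Section 12.0, Aim 1, plans one comparison of limbs, a two-way mixed MANCOVA or non-parametric equivalent, which "will be used to test for statistically significant differences in strength and endurance between legs" (prosthetic, intact and control) and across muscle groups. The other Aim 1 model, a multiple regression, is confined to prosthesis users. The power paragraph sets power at 0.80 and alpha at 0.05 and states that a group size of 20 "will be sufficient to identify differences (p<0.05) in hip muscle strength and endurance between the residual limb, intact limb, and able-bodied persons".

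Section 12.0 also provides that "Measures of central tendency and variation will be used to describe participant characteristics, and all study variables". It names 95% confidence intervals and effect sizes only for Aim 2.

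**The concern.** A claim of no difference cannot be supported by failing to find one. The planned analysis does not fit hypothesis (ii) in either direction.

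- **Significant leg effect.** The test spans three kinds of leg. If hypothesis (i) is true and the residual limb is weaker, the leg effect can be significant for that reason alone. Without a named intact-control contrast, the result says nothing definite about (ii).
- **Non-significant result.** This fits equality, but it also fits a moderate intact-limb deficit that 20 per group did not detect.

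At stake is one of the two numbered Aim 1 hypotheses. At the end of the study there would be no pre-specified basis for saying whether it was supported, and a non-significant p-value could easily be reported as if it were that basis.

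**Working it through.** **The logical step** needs no figures. The hypothesis asserts equality, the analysis seeks differences, the power statement concerns finding differences, and no margin, equivalence test or interval rule is given for intact against control. The arithmetic below only shows the scale.

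**Inputs from Section 12.0:** 20 per group, power 0.80, alpha 0.05. **Assumed, because the documents do not give them:** a two-sided test, one endpoint, a common SD of 1, a simple two-group comparison without covariates, the true differences and margins in SD units, and within-pair correlations r of 0.3 or 0.5 where matching is used.

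**1. The plan's own figure.** The 20 per group cannot be reproduced. It rests on pilot data from two people per group, with no effect size or SD reported. Solving backwards for a two-group comparison, the difference detectable with 80% power is (1.960 + 0.842) × √(2/20) = 0.89 SD, or 0.91 SD with the t distribution.

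**2. Chance of a non-significant result when the intact limb is truly weaker.**

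Independent groups: P(|T| < 2.024), with T noncentral t on 38 df and noncentrality d√(20/2).
- d = 0.3: noncentrality 0.95, non-significant 85%
- d = 0.5: noncentrality 1.58, non-significant 66%
- d = 0.8: noncentrality 2.53, non-significant 31%

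Matched pairs: SD of the difference = √(2(1 − r)), 19 df, critical value 2.093, true deficit 0.5 SD.
- r = 0.3: SD 1.183, noncentrality 0.5√20/1.183 = 1.89, non-significant 57%
- r = 0.5: SD 1, noncentrality 0.5√20 = 2.24, non-significant 44%

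**3. Precision of the intact-control difference (confidence interval half-width).**
- Independent, 95%: 2.024 × √(2/20) = 0.64 SD
- Independent, 90%: 1.686 × √(2/20) = 0.53 SD
- Paired, 95%: 2.093 × 1.183/√20 = 0.55 SD (r = 0.3); 2.093/√20 = 0.47 SD (r = 0.5)
- Paired, 90%: 1.729 × 1.183/√20 = 0.46 SD (r = 0.3); 1.729/√20 = 0.39 SD (r = 0.5)

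With independent groups and the assumed SD, a margin below 0.53 SD could not be met even if the observed difference were exactly zero.

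**4. What an equivalence claim would need.** Two one-sided tests at 5% each, true difference zero.
- Margin for 80% power, normal approximation, independent groups: (1.645 + 1.282) × √(2/20) = 0.93 SD
- The same allowing for the estimated SD: 0.94 SD independent, 0.80 SD (r = 0.3), 0.68 SD (r = 0.5)
- Power at a 0.5 SD margin with 20 per group: 3%, 17.5% and 39% respectively
- Sample for 80% power at a 0.5 SD margin: 70 per group, 50 pairs and 36 pairs respectively

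**The case against.** The strongest reply is that little depends on (ii). The central hypothesis concerns the residual limb and socket design and makes no claim that intact limbs equal controls. The figures model one unadjusted endpoint on assumed effect sizes, whereas the plan is multivariate, covariate-adjusted and uses matched controls. All of this stands. It limits the weight of the point and means the numbers are illustrative, but it does not supply the missing basis for (ii).

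A second reply is that descriptive statistics are planned for all variables. An unadjusted intact-control difference could indeed be derived from them. That is description, not a rule for when (ii) is supported.

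A third is that an equivalence test is close to unusable at 20 per group, and that a rule applied outcome by outcome would not settle (ii) as a whole. Section 6.0 gives four muscle groups and three measures (peak torque, rate of torque development, fatigue index), so 4 × 3 = 12 outcomes. This stands too, and is why estimation should lead the remedy.

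A reader might also infer more than the documents support:

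- *That the investigators will read p > 0.05 as equality.* The plan nowhere says so. The gap is that it offers no other criterion.
- *That the planned test could at least contradict (ii).* As written this is not secured, because contradicting (ii) would need an intact-control contrast after the omnibus test.
- *That the power statement overlooks the intact-control comparison.* It includes it, but for identifying differences only.
- *That the Section 2.0 argument against general deconditioning rests on (ii).* That argument says of the residual limb that "These changes are not observed with the same frequency or magnitude in the intact leg". It is a residual-intact contrast, which belongs to hypothesis (i) and does not require the intact limb to equal controls.

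Whether the analysis should exploit the matching, and how to handle covariates that controls cannot have, are separate questions and add nothing here.

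**Conclusion.** The point holds as a mismatch between a stated hypothesis and its stated analysis. Followed as written, the plan cannot support hypothesis (ii), and without a named contrast it does not clearly test it either. This conclusion is one of logic and rests on no assumed figure.

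Its practical size does rest on the assumptions listed in the working. On those, a real half-SD intact-limb deficit would go undetected in roughly two studies in three with independent groups, and in about half with a paired analysis and effective matching. The change is worth making before analysis. It is no criticism of the central hypothesis, hypothesis (i) or Aim 2.

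**What to change.** In Section 12.0, Aim 1, name the intact-control contrast and restate (ii) as estimation. Suggested text:

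> *For hypothesis (ii), the difference between the intact limb and matched controls will be estimated and reported with its 95% confidence interval for each strength and endurance outcome. These intervals are descriptive and not adjusted for multiplicity. A non-significant result will not be read as no difference.*

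Add to the power paragraph:

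> *The stated power of 0.80 refers to detecting differences, not to showing equivalence.*

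Bring the wording of (ii) in Section 3.0 into line. Only if the investigators can justify an equivalence margin before the data are analysed should an outcome be described as not differing. Even then, this should apply only when that outcome's 90% confidence interval lies within the margin, and to that outcome alone.

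**Cost:** a few lines of text and one decision on whether a margin can be justified; no extra participants. **Downside:** (ii) will probably end as an estimate rather than a confirmed claim, because the margins that 20 per group can support are wide.

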4.0 Eligibility

The target population for the proposed study is adult unilateral lower limb prosthesis users whose amputation is due to traumatic, dysvascular, or oncologic reasons. We will not exclude participants based on age, race, sex, or ethnicity. In an effort to recruit and include under-represented minorities will we monitor participant demographics during the study and adjust our efforts as necessary to improve the inclusion of under-represented groups.

We will recruit lower limb prosthesis users in Chicago from Scheck and Siress Prosthetics and Orthotics. Scheck and Siress have over a dozen clinics in the Chicagoland area. Their offices regularly treat more than 2000 lower limb prosthesis users a year. Clinicians at Scheck and Siress will only participate in passive recruitment, sharing information about current research participation opportunities with patients. We may recruit from other clinics in the Chicagoland area if recruitment proves to be challenging.

Participant eligibility will be evaluated and determined by the investigators or research staff using specific inclusion and exclusion criteria via in-person or phone interviews. In person interview will occur in any of three locations:

1. Disability, Health, and Social Policy Building, Room 198 [name]

2. Applied Health Science Building, [name]

4.1 Inclusion Criteria

Inclusion criteria for lower limb prosthesis users will be: 1) worn prosthesis for ≥ 2 years, 2) able to walk short distances (10 meters), 3) ability to read, write, and speak English, and for Aim 2 only, ≥ 2 years using a liner-based suspension, and a residual limb length ≥ 5 ". Inclusion criteria for unimpaired controls will be: 1) ability to read, write, and speak English, 2) between the ages of 18-85 years of age, and 3) able to walk short distances (10 meters).

4.2 Exclusion Criteria

Exclusion criteria will be: 1) amputation of a second leg, 2) contralateral complications (e.g., hip replacement), or 3) other major neuromusculoskeletal or cardiovascular conditions (e.g., heart failure). Age- and sex-matched able-bodied persons will be recruited from the community for Aim 1 with non-amputation related criteria applicable (e.g., major neuromusculoskeletal or cardiovascular conditions).

4.3 Excluded or Vulnerable Populations

Subjects younger than 18 and older than 85 years of age will be excluded, as their inclusion would introduce confounding factors of sensorimotor changes due to motor development and aging.

Subjects for whom English is a second language will also be excluded because there are extensive verbal instructions that must be provided to the participants. Translation services are not readily available to assist laboratory personnel. Participants will also be expected to provide information via self-report survey instruments that have not been translated and/or validated in other languages.

Individuals with bilateral lower limb loss and any upper extremity limb loss will be excluded, as their biomechanics are not comparable to individuals with unilateral lower limb loss.

5.0 Subject Enrollment

Lower limb prosthesis users will be recruited from prosthetics clinics in Chicago via flyers or information about the study provided to them by clinic staff during clinic visits._Age- and sex-matched able-bodied persons will be recruited from the community via flyers placed on the UIC campus.

To minimize coercion or undue influence over the patient population of interest, lower limb prosthesis users, it will be communicated to them that their clinical care does not depend in any way on whether they elect to participate or not in this research study.

If an individual shows interest in participation in the study, we will obtain general health information from them to confirm that they are eligible for study participation. General health information will include age, weight, and self-reported medical history, including if they have any vision impairments, balance impairments, cognitive impairments, progressive neurological conditions, or any other major motor or sensory dysfunction or medical condition. This screening process could talk place via a telephone interview or in person. Regardless of the method, screening will be done in a private room to protect participant's confidentiality. After participants review and sign consent forms on the day of the assessment, we will obtain more detailed health information during an interview using several surveys and questionnaires.

Any data that is collected from participants who are not eligible or interested in participating in the study will be deleted from our records. Electronic data will be permanently erased from the stand alone PC on which it is collected. Any hard copies will be shredded.

6.0 Study Design and Procedures

Consented individuals will participate in 1 or 3 test sessions. Each session will require approximately 3 hour. For Aim 1, we will conduct a cross-sectional study to evaluate residual and intact limb hip muscle function in lower limb prosthesis users compared to able-bodied persons. All participants will be administered characterization measures, balance and mobility tests, as well as a series of procedures to evaluate hip muscle strength, endurance, and coordination. This will require a single 3-hour test session. Able-bodied controls and lower limb prosthesis users will perform the same activities in Aim 1.

For Aim 2, we will conduct a pilot within-subjects study to assess if walking with a different socket alters residual limb hip muscle function. In Aim 2, a sub-set of lower limb prosthesis users from Aim 1 will walk with a different socket. These participants will be selected on the basis of meeting the inclusion and exclusion criteria specified above for Aim 2. The same measures, tests, and procedures from Aim 1 will be administered in Aim 2 at two time points, eight and 42-weeks after baseline testing. Outcomes at these two time points will be compared to baseline (Aim 1) to evaluate differences in hip muscle function associated with walking in a different socket. Three total test visits will be required of participants in Aim 2.

The tasks listed below will be performed at each visit.

Characterization Measures: Sociodemographic, health, falls history (all subjects), and prosthetic-related information (prosthesis users only) will be collected using psychometrically robust self-report outcomes to characterize study participants. This will include age, general health (PROMIS 29), residual limb length, cause and time since amputation, mobility (Prosthetic Limb Users Survey-Mobility), socket comfort (Socket Comfort Score), and balance confidence (Activities-specific Balance Confidence Scale). Falls history will be obtained by asking participants "*in the past year have you inadvertently lost your balance and landed on the ground or lower level?*". Amputation surgical techniques (e.g., muscle fixation) may vary across participants, and confound assessments of residual limb hip muscle function. In an effort to obtain this data we will create a permission form to be signed by the participant and sent, along with a short survey, to their surgeon requesting basic information about the amputation procedure (e.g., myoplasty versus myodesis).

